## 1.2 Objective

---

The principal objective of this study is to prospectively follow glaucoma suspects (GS) with depressed PERG amplitude, either in SSP or upon HDT, who have been randomized either to observation or to receive either pressure lowering medicines and compare them with respect to longitudinal RNFL thinning from baseline. Further objectives include confirmation of previously published and unpublished findings suggesting that: pressure lowering medicines improve PERG amplitude in eyes with depressed SSP PERG amplitude; substantially depressed SSP PERG amplitude is a risk factor for more rapid RNFL thinning in eyes not receiving pressure lowering medications; and that delayed PERG phase upon HDT in combination with hemodynamic measurements is predictive of RNFL thinning in eyes not receiving pressure lowering medications.

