## 2.5 Analysis and Sample Size Calculations

---

Percentages of patients with RNFL thinning after four years of follow up will be compared between the observation and pressure lowering medicine groups. RNFL thinning is defined as a decrease in average RNFL of  $4.0\mu\text{m}$  (Budenz, (Invest Ophthalmol Vis Sci. 2010;51:5724 –5730)).

Preliminary data suggest that about 40% of untreated patients in stratum 1 (GS-A) will have incident RNFL thinning, while about 60% of untreated patients in

stratum 2 (GS-S) will have incident RNFL thinning. These data also suggest that about 15% of patients in stratum 3 (GS-N) will have incident RNFL thinning.

If pressure lowering medicines reduce the risk of RNFL thinning in patients in strata 1 and 2 to 15%, then about 32 patients in each randomized treatment group would provide 80% power. 42 patients in each randomized treatment group would provide 90% power.

If pressure lowering medicines do not reduce the risk of thinning to 15% but only to half the risk in the untreated patients, then 66 patients in each group would provide 80% power.

These calculations assume separate independent un-corrected significance tests in each stratum. If pressure lowering medicines had similar effects in each stratum, a pooled analysis would have substantially more power.

---

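### Section 2.5 gives one sample size per scenario for separate tests in two strata with different risks; GS-A power is about 50–75%, not the stated 80–90%

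*Combined protocol and SAP*

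**What the plan says.** All of the power reasoning is in Section 2.5 (Analysis and Sample Size Calculations). The endpoint is binary: RNFL thinning at four years, compared between observation and pressure-lowering medicine.

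- **Untreated risks.** For GS-A: "Preliminary data suggest that about 40% of untreated patients in stratum 1 (GS-A) will have incident RNFL thinning". For GS-S, the section puts the corresponding figure at about 60%.
- **Scenario 1.** Treatment lowers the risk to 15% in both strata: "then about 32 patients in each randomized treatment group would provide 80% power", and "42 patients in each randomized treatment group would provide 90% power".
- **Scenario 2.** Treatment only halves the untreated risk: "then 66 patients in each group would provide 80% power".
- **Unit of testing.** "These calculations assume separate independent un-corrected significance tests in each stratum". The section then says that, if effects were similar across strata, "a pooled analysis would have substantially more power".

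The section names no test, alpha, sidedness or dropout allowance. Section 7.3 sets equal allocation.

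**The concern.** The two strata have different untreated risks, so the effect to be detected differs: 40% against 15% in GS-A and 60% against 15% in GS-S or, if risk is halved, 40% against 20% and 60% against 30%. A single size per group cannot give 80% power for both members of either pair, whatever the test or alpha. Yet the section attaches one size and one power to each scenario and says the tests are done stratum by stratum.

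Both strata matter. The principal objective in Section 1.2 covers suspects with "depressed PERG amplitude, either in SSP or upon HDT", and both strata are randomised. Anyone choosing a size from Section 2.5 would get less power than stated in GS-A and more in GS-S. A null result in GS-A could then be read as a negative finding at 80–90% power when the real chance of detecting the assumed effect was much lower.

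**Working it through.** **Inputs.** From Section 2.5: untreated risks 0.40 (GS-A) and 0.60 (GS-S); treated risk 0.15, or 0.20 and 0.30 if halved; sizes 32, 42 and 66 per group. From Section 7.3: 1:1 allocation. Assumed: two-sided alpha 0.05, no dropout.

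**Formulas.** With d = p1 − p2 and p̄ = (p1 + p2)/2, the size per group without continuity correction is

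n = [1.960·√(2p̄(1−p̄)) + z·√(p1(1−p1) + p2(1−p2))]² / d²,

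where z = 0.842 for 80% power and 1.282 for 90%. With continuity correction it is

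n_cc = (n/4)·[1 + √(1 + 4/(n·d))]².

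**Step 1: where the plan's figures may come from.** Neither stratum's own risk yields 32, 42 and 66 together. The midpoint risk of 50% does, with continuity correction:

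- 50% v 15%, 80% power: n = (1.2982 + 0.5171)²/0.35² = 26.9; n_cc = 32.4 (plan: about 32).
- 50% v 15%, 90% power: n = 35.5; n_cc = 41.0 (plan: 42).
- 50% v 25%, 80% power: n = 57.7; n_cc = 65.4 (plan: 66).

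This origin is an inference, because the plan mentions neither a 50% risk nor a continuity correction.

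**Step 2: sizes at the plan's own stratum risks.** For example, GS-A at 80% power, 40% v 15%: n = (1.2377 + 0.5102)²/0.25² = 48.9; n_cc = 56.6. All results, rounded up, as uncorrected / corrected:

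| Target | Plan | GS-A needs | GS-S needs |
|---|---|---|---|
| 80%, treated risk 15% | 32 | 49 / 57 | 17 / 22 |
| 90%, treated risk 15% | 42 | 65 / 73 | 23 / 27 |
| 80%, risk halved | 66 | 82 / 91 | 42 / 49 |

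**Step 3: power at the plan's sizes.** Exact power was found by enumerating both binomial distributions and summing the probability of every outcome pair that rejects. The range runs from the continuity-corrected chi-square (low) to the uncorrected chi-square (high); Fisher's exact test falls within it.

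| Size per group | Stated | GS-A | GS-S |
|---|---|---|---|
| 32 (treated 15%) | 80% | 50.4–63.2% | 95.6–97.7% |
| 42 (treated 15%) | 90% | 64.8–74.9% | 99.0–99.5% |
| 66 (risk halved) | 80% | 65.0–71.6% | 91.1–93.7% |

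**Step 4: sensitivity to sidedness.** At one-sided 0.05, GS-A power is 63.2–75.0%, 77.3–84.2% and 76.0–81.9%. Only the figure for 66 can then be met, and only without continuity correction.

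**Step 5: the pooled reading.** Suppose 32, 42 and 66 were totals per arm, split equally between the strata (an assumption), and analysed with a stratified continuity-corrected Cochran–Mantel–Haenszel test. Simulation with 200,000 replicates gives power of 80.6%, 91.5% and 81.6%, close to the stated 80%, 90% and 80%. With those sizes in each stratum, the same pooled test has at least 98.7% power.

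**The case against.** The best counter-argument is that the sizes were meant as pooled totals. Section 2.5 opens by comparing the two treatment groups without mentioning strata, the sizes are given per randomised group, and step 5 shows that pooled totals deliver almost exactly the stated power. On that view the numbers are sound and the wording is wrong. This is a real possibility, but it contradicts both closing sentences of the section: the one on separate tests, and the one that treats pooling as an extra source of power. The section therefore needs correcting on either reading.

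The other objections carry less weight:

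- **Un-corrected may mean no continuity correction.** The more natural meaning is no multiplicity adjustment. Even so, only the upper ends of the ranges would then apply: 63%, 75% and 72%, all still short.
- **Alpha and sidedness are assumed.** That is true. One-sided 0.05 rescues only the 66 figure, and 32 and 42 per group still miss by 5 to 6 points at best.
- **The risks are approximate.** At 45% untreated risk in GS-A, uncorrected power would be about 77%, 87% and 80%, close to the stated values. This shows how sensitive the claim is, but 40% is the plan's figure.
- **The 50% origin fits imperfectly.** Rounding 32.4 up gives 33, not 32. The finding does not depend on that origin.
- **The consequence is limited.** The available text fixes no enrolment target, and a pooled analysis with these sizes in each stratum would be amply powered. Both points are fair, but the section does not make the pooled analysis the basis of its power figures.

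**Conclusion.** The concern holds. Read as written, Section 2.5 overstates power in GS-A at every quoted size: by about 17 to 30 percentage points at 32 per group (80 against 63.2–50.4), 15 to 25 at 42 (90 against 74.9–64.8) and 8 to 15 at 66 (80 against 71.6–65.0). Power in GS-S is understated.

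The sizes of these gaps rest on two-sided 0.05, the plan's 40% risk and complete follow-up; any loss over four years would reduce power further. That one size cannot serve both strata rests on none of these assumptions. What is shown is a wrong power statement at each quoted size. It is not shown that the trial enrolled too few patients.

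**What to change.** Restate Section 2.5 by stratum, naming one test, alpha and sidedness throughout. Give the size each stratum needs (the step 2 table supplies both versions at two-sided 0.05) and report the actual power in GS-A and GS-S at 32, 42 and 66 per group.

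If the sizes were intended as totals per arm for one pooled GS-A plus GS-S comparison at an average 50% risk, say so, and revise both the sentence on separate tests and the one on the gain from pooling.

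Either route changes protocol wording only. On the by-stratum route, all three GS-A power figures become less favourable. No extra enrolment is needed to make the statement correct. Reaching the stated power in GS-A would take 49–57 per group instead of 32, 65–73 instead of 42, and 82–91 instead of 66, before any allowance for dropout.

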## 2.6 Masking

---

Neither the investigator nor the patient is masked as to which treatment the patient receives.

---

## 2.7 Timetable for the Study

---

- **Year 1: Validate new PERG instrument, including normal control values. Complete baseline measurements, place patients into study strata and randomize GS-A and GS-S patients**
- **Year 2-4: Collect follow up visit data, monitor for pressure lowering in those patients randomized to receive pressure lowering therapy**
- **Year 5: Collect final follow up visit data and perform analyses**

#### **3.1 Visual Acuity**

---

Visual acuity is measured before pupil dilation, tonometry, gonioscopy, or any other technique that could affect vision. Refraction is performed prior to formal measurement of visual acuity by either technique at the Qualifying Assessment and at the annual follow-up visits. Snellen visual acuity is measured at the Qualifying Assessment and at every follow-up visit.

##### **Subjective Refraction:**

Subjective refraction must be performed at the Qualifying Assessment and at the annual follow-up visits in order to determine best-corrected visual acuity. It is permissible to use a phoropter to determine best-corrected Snellen visual acuity. However, trial frames are required for testing best-corrected visual acuity. The trial frame is placed and adjusted on the patient's face so that the lens cells are parallel to the anterior plane of the orbits and centered in front of the pupil.

The left eye is occluded first. An approximate beginning refraction may be determined by retinoscopy, automated refraction, or a subjective refraction from a prior visit. The sphere is refined first. The cylinder is then refined, first the axis followed by the power. Finally, the sphere is rechecked. If a phoropter was used in the subjective refraction, the refraction is placed in a trial frame and the sphere is refined prior to visual acuity testing. The right eye is then occluded, and the procedure is repeated for the left eye.

If the patient wears contact lenses and has glasses also, he or she is instructed not to wear the contact lenses on the day of the Qualifying Assessment. In the event that the patient either has no glasses or has forgotten the instructions and reported for the Qualifying Assessment wearing contact lenses, the contact lenses are removed and at least thirty minutes allowed to elapse before subjective refraction and visual acuity testing is performed.

### **Snellen Visual Acuity:**

Snellen visual acuity may be measured using any standard visual acuity chart. The same type of chart must be used throughout the duration of the study. Snellen visual acuity is measured during the Qualifying Assessment and at all follow-up visits. Standardized refraction is performed prior to Snellen visual acuity testing at the Qualifying Assessment and annual follow-up examinations.

## **3.2 Slit Lamp Biomicroscopy**

---

Examination of the anterior segment using slit lamp biomicroscopy is performed at the Qualifying Assessment to document the status of the eye, and at all follow-up examinations to detect any changes in the conjunctiva, cornea, anterior chamber, iris, and lens that may be attributable to the disease or treatment. Slit lamp biomicroscopy may be performed with any commercially available instrument, and it is used in a standard fashion starting anteriorly and working posteriorly. Standardizing opacities is difficult, but it is expected that subjective grading by the optometrist or glaucoma specialist is relatively reproducible. Pseudophakic eyes with uncomplicated cataract extraction are included in the study. Aphakic eyes are excluded from the study.

### 3.3 Tonometry

---

Goldmann applanation tonometry is used to measure the intraocular pressure, except when irregular corneal astigmatism, corneal scarring, or corneal edema precludes accurate readings. The intraocular pressure is measured prior to pupillary dilation. Whenever possible, the intraocular pressure should be checked at the same time of the day as the Qualifying Assessment to minimize the effect of diurnal fluctuation of intraocular pressure.

#### **Goldmann Applanation Tonometry:**

The calibration of the Goldmann applanation tonometer is checked every 3 months, as described in the Haag-Streit Goldmann Applanation Tonometer Operator's Manual. Clean the prism according to your institutional infection control policy. The right eye is always tested first. Following instillation of a drop of 0.5% proparacaine, a fluorescein strip is placed near the lateral canthus in the lower conjunctival sac. Once the lacrimal fluid has been sufficiently colored, the fluorescein strip is removed. Alternatively, one drop of premixed fluorescein and anesthetic may be instilled. The patient's head is properly positioned in the chin rest and against the forehead rest without leaning forward or straining. Any tight-fitting neckwear is loosened. The patient is asked to look straight ahead at a distant object or fixation target. If it is necessary to hold the eyelids open, the investigator holds the eyelids open against the orbital rim taking care not to apply any pressure on the globe. The patient is instructed not to hold his or her breath. If corneal astigmatism is greater than 3.0 diopters, the prism is rotated so that the axis of the minus cylinder on the prism graduation corresponds to the red mark on the prism holder. The investigator looks through the slit lamp and gently brings the tip of the prism in contact with the center of the cornea. The mires should be well focused, centered horizontally, and positioned vertically so that they are of equal circumference above and below the horizontal dividing line. If the mires are narrower than approximately one tenth their diameter, the investigator instills additional fluorescein. The investigator adjusts the measuring drum until the inner borders of the two mires just touch each other. If pulsation is present, the measuring drum is adjusted until the mires separate a given distance during systole and overlap the same distance during diastole. The investigator removes the prism from the cornea and repeats the procedure in the right eye until two successive measurements are within 1 mm Hg. The investigator records the last two successive measurements. After testing of the right eye is complete, testing of the left eye follows the same technique.

#### **PT100:**

The PT100 (Reichert) is portable, non contact tonometer that is used to compare IOP between SSP and HDT position. The patient is positioned in either sitting

position or HDT position and instructed to fix on a distant object. Tight-fitting neckwear is loosened, and the patient is instructed not to hold his or her breath. The operator used the instrument as an ophthalmoscope and aims the light beam toward the patient's pupil. PT100 visual indicators guide the operator to correct alignment position. Once alignment is achieved the PT100 automatically takes an IOP measurement, that is perceived by the patient as an light air puff on the cornea. Three sequential measurements are required, and the instrument automatically calculates the average and the SD. The right eye is always tested first.

### **3.4 Gonioscopy**

---

Gonioscopy is performed with the patient sitting at the slit lamp using either a Zeiss type four-mirror gonioprism or Goldmann single- or three-mirror lens. An examination of the anterior chamber angle for neovascularization is performed under high magnification for the purpose of excluding eyes with neovascularization from the study.

### **3.5 Ophthalmoscopy**

---

A dilated fundus examination is performed at the Qualifying Assessment to determine the status of the retina and optic nerve, and at all one-year follow-up examinations to detect any changes. After pupil dilation with appropriate mydriatics, the optic nerve and posterior pole are examined at the slit lamp using a Hruby lens, fundus contact lens, or Volk 90 diopter, 78 diopter, or 60 diopter lens. A head-mounted indirect ophthalmoscope and hand held condensing lens (20 diopter or 28 diopter Nikon aspheric lens) is used to evaluate the retinal periphery. At the Qualifying Assessment, particular attention is paid for signs of macular degeneration that represent an exclusion criterion.

### **3.6 Corneal Thickness Measurement**

---

Central corneal thickness is measured with ultrasound pachymetry at the first baseline exam. The right eye is tested first. A drop of 0.5% proparacaine is instilled for anesthesia. The patient is asked to look straight ahead at a distant object or fixation target. The pachymeter probe is lined up with the center of the pupil and slowly advanced until it contacts the cornea. The probe is withdrawn when an audible signal is made indicating that a measurement has been

recorded. The patient is instructed to blink. The procedure is repeated to obtain three separate readings, and the investigator records the measurements. After testing of the right eye is complete, the same technique is applied to testing of the left eye.

### **3.7 Perimetry**

---

Quantitative automated perimetry is performed using the Humphrey Field Analyzer . Visual field testing is performed before tonometry, gonioscopy, or any other technique that could affect vision.

A 24-2 threshold test is performed in all patients using a size III white stimulus. Visual field testing may be performed with the Swedish Interactive Thresholding Algorithm (SITA) or full threshold strategy, but the same testing strategy must be used throughout the duration of the study. The pupil diameter should be 3 mm or greater before visual field testing is undertaken, and this may require pharmacologic dilation. Standardized refraction is performed to determine the patient's distance refraction and best-corrected visual acuity prior to visual field testing. The age appropriate plus lens is added to the distance refraction. Patient education is provided, and the instrument is set up for the test. The technician should monitor the patient during testing. Visual fields are performed preoperatively (within one month of enrollment in the study) and annually thereafter. Copies of all visual fields are faxed to the Statistical Coordinating Center for evaluation.

### **3.8 Optical Coherence Tomography**

---

Quantitative image analysis of the retinal nerve fiber layer (RNFL) and Ganglion Cell (GCA) is performed with Zeiss-Cirrus according to the protocol of (Mwanza et al, Ophthalmology 2012, 119:1151-1158). Cirrus HD-OCT is used to acquire 1 macular (Macular Cube 200×200 protocol) and 1 optic disc (Optic Disc Cube 200×200 protocol) scan in each qualifying eye after pupil dilation with tropicamide 1% and phenylephrine 2.5%. Only good-quality scans, defined as scans with signal strength  $\geq 6$ , without RNFL discontinuity or misalignment, involuntary saccade or blinking artifacts, and absence of algorithm segmentation failure on careful visual inspection, are used for analysis. Peripapillary RNFL thickness analysis includes the average, superior, and inferior quadrant thicknesses. Parameters from the ONH analysis include the rim area, cup-to-disc area ratio, and vertical cup-to-disc diameter ratio, which were measured automatically by the Cirrus internal ONH analysis algorithm. The GCA algorithm detects and measures the thickness of the macular GCIPL within a 14.13-mm^2 elliptical

annulus area centered on the fovea. The following GCIPL thickness measurements are analyzed: average, minimum, and sectoral (superior, superonasal, inferonasal, inferior, inferotemporal, and superotemporal).

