## 5.3 Biostatistics Center

---

The study statistician for the Stop-RGCD study, [name] and **[name]**, has the following responsibilities:

- Creation of the variable permuted block randomization lists for the GS-A and GS-S strata.
- Running interim edit checks of study data.
- Performing data analyses and preparing manuscripts with the project chairman.
- Ensuring security of patient data transmitted to the biostatistics center.

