## **7.3 Randomization Procedure**

---

Randomization takes place at the time the patient is enrolled in the study. After patient eligibility is confirmed and a patient identification number is provided, the Statistical Coordinating Center assigns treatment by saying, “Treatment” or “No Treatment”. The Clinical Center then repeats the assigned treatment. The treatment/no treatment date is the study entry date, and the dates for all follow-up visits are computed from this date.

The randomization schedule is constructed using a computer pseudo-random number generator. The allocation ratio is equal between the two treatment groups. The randomization is blocked by clinic and study stratum using a scheme with small variable blocks. This procedure ensures that there is an equal number of patients in each treatment group even early in the trial, and that the CC is not able to predict the next treatment assignment.

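### OCT scans enter the main endpoint after a partly subjective visual check, and the open-label plan specifies no masked scan inspector

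*Combined protocol and SAP*

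**What the plan says.** Section 2.5 sets the main comparison: "Percentages of patients with RNFL thinning after four years of follow up will be compared between the observation and pressure lowering medicine groups". The outcome is binary with a hard cut-off: "RNFL thinning is defined as a decrease in average RNFL of" 4.0 µm.

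Section 3.8 restricts which scans can supply that measurement. It begins "Only good-quality scans, defined as scans with signal strength" of at least 6. It then requires no RNFL discontinuity or misalignment, no saccade or blink artefact, and "absence of algorithm segmentation failure on careful visual inspection, are used for analysis". The person who inspects is not named. One optic disc scan per qualifying eye is specified, and nothing is said about what happens when it fails.

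Section 2.6 is one sentence: "Neither the investigator nor the patient is masked as to which treatment the patient receives". Assignments come from the coordinating center by voice (7.3: "the Statistical Coordinating Center assigns treatment by saying"). Section 5.3 gives the statisticians the task of "Performing data analyses and preparing manuscripts with the project chairman". No masked OCT reader, reading center or masked analyst is described.

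The visit table in 7.4 appears to schedule OCT both at the year-4 visit and at a year-4 repeat visit. No rule says which of the two supplies the endpoint.

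**The concern.** The thickness value comes from the instrument, so the endpoint looks protected from observer bias. The decision whether that value is used is made by a person. Signal strength is a number, but judging segmentation failure is left to the eye. A failed segmentation and a truly thin layer can both give a low reading. An inspector who sees a low value and knows the arm could, in good faith, lean towards artefact in one arm and disease in the other.

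Because the outcome is dichotomised at 4.0 µm and groups may be as small as 32, a handful of such decisions can move the percentages being compared. With no rule for repeating a failed scan or choosing between two year-4 scans, there is further room for discretion after the arm is known. At stake is the credibility of the trial's main result, even if every decision was sound.

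**Working it through.** **What the plan gives.** It states no scan rejection rate, so there is no figure of its own to reproduce on this point. The rates below are assumptions. From 2.5 come the untreated thinning risk in stratum 1 (40%) and the smallest and largest group sizes (32 and 66). The test level is not stated; I assume two-sided 5%.

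**Group sizes.** The stated 32, 42 and 66 are reproduced to within one patient (33, 42, 66) by a two-sided 5% test with continuity correction and an untreated risk of 50%, midway between the two strata. That 50% is inferred. Here the sizes serve only as inputs.

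**Scenario.** There is no true effect and the thinning risk is p = 0.40 in both arms. A share r of thinned treated-arm scans is rejected and lost, and nothing else is rejected.

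Apparent treated risk = p(1 − r) / (1 − pr):

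- r = 10%: 0.36 / 0.96 = 37.5%
- r = 20%: 0.32 / 0.92 = 34.8%
- r = 30%: 0.28 / 0.88 = 31.8%

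Expected scans lost = n × 0.40 × r. At n = 66 this is 2.6, 5.3 and 7.9, and at n = 32 it is 1.3, 2.6 and 3.8. The treated denominator must shrink by these losses.

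**Rejection rate of the test.** I used exact enumeration of the uncorrected Pearson chi-squared test. The number m of accepted treated scans is binomial (n, 1 − pr). Given m, the thinned count x is binomial with the apparent risk above. The observation count y is binomial (n, 0.40). The test rejects when |x/m − y/n| / √[p̄(1 − p̄)(1/m + 1/n)] ≥ 1.96, with p̄ = (x + y)/(m + n).

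| Share rejected, r | Apparent treated risk | 66 per arm | 32 per arm |
|---|---|---|---|
| 0% | 40.0% | 5.0% | 5.6% |
| 10% | 37.5% | 6.0% | 5.7% |
| 20% | 34.8% | 9.3% | 7.2% |
| 30% | 31.8% | 15.7% | 10.3% |

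**Hand check by normal approximation, r = 20%, n = 66.** The expected treated denominator is 66 × 0.92 = 60.72. The pooled risk is (21.12 + 26.4) / 126.72 = 0.375. The null standard error is √[0.375 × 0.625 × (1/60.72 + 1/66)] = 0.0861, and the alternative standard error is 0.0859. The difference is 0.400 − 0.348 = 0.052. The two tails are Φ(−1.36) + Φ(−2.57) ≈ 0.087 + 0.005 = 9.2%, in line with 9.3%.

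**Sensitivity (normal approximation).** With 60% thinning in both arms, the stratum 2 figure, r = 20% gives 9.4% at 66 per arm and 7.1% at 32. If the inspector also rejects 20% of non-thinned observation-arm scans, the rates at 40% thinning are 21.9% and 13.0%.

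**The case against.** - **The thickness is automatic and the criteria are explicit.** This stands in part. Signal strength is numeric, the other criteria are image features unrelated to arm, and the visual-inspection wording attaches most directly to segmentation failure. The room for judgement is limited, but it is not nil.
- **Exposure is confined.** Baseline OCT is scheduled at the baseline visits, so the route is mainly at follow-up. This stands.
- **The scenario is one-sided and assumes permanent loss.** This stands as a limit on the illustration. At 10% rejection the inflation is about one percentage point at 66 per arm and negligible at 32. The apparent year-4 repeat OCT could rescue a rejected scan, though with no rule on which scan counts it also adds a choice.
- **A safeguard may be written elsewhere.** Section 3.8 follows a cited OCT protocol that could not be read, and the Clinical Centers section is not in the copy reviewed. This is uncertainty, not evidence of a safeguard.
- **An existing team member may not stay unaware of the arm.** Staff meet quarterly on study progress (5.4). The point is fair, and the fix therefore relies on ID-only scans and on someone who does not manage the patient.

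A reader might go further and infer that nobody in the trial is masked. Section 2.6 names only the investigator and the patient, and 3.8 names no inspector, so the documents support only that no masked inspector is specified. A reader might also infer that such bias could never be detected afterwards. Nothing says rejected scans are destroyed, and counts by arm or a later masked re-read could show a gross imbalance. The plan simply requires neither.

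**Conclusion.** The gap is real and modest. A partly subjective acceptance step decides which OCT scans feed the main endpoint, investigator and patient know the arm, and no masked inspector is specified. The documents show that bias is possible; they do not show that it occurred or is likely.

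The size depends wholly on assumed rejection rates. Losing about five thinned treated-arm scans out of 66 patients (20%) would take a nominal 5% error rate to about 9.3%. At 32 per arm the same share gives 7.2%, against 5.6% with no bias. These figures assume rejection only of thinned scans, only in the treated arm, with no replacement. With no arm-dependent rejection there is no inflation. The safeguard is worth adding because it is cheap and protects the main result. The trial's open-label treatment is not itself at fault.

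**What to change.** Add to 2.6 and 3.8:

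1. Scan acceptance is decided by an existing study team member who does not manage the patient. That person works from scans labelled by study ID only, without arm, and decides before the RNFL change from baseline is displayed.
2. A rejected scan is repeated under the same rule in both arms. A pre-specified rule states which year-4 scan, first or repeat, supplies the endpoint.
3. Every rejection and its reason is logged, and counts are reported by arm.

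The cost is a few protocol sentences, ID-only export of scans, a log, and a short delay because the treating clinician no longer makes the final decision. Treatment, endpoint definition and sample size are unchanged.
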